## Variables

Variable	Definition	Type	Scale
Primary outcome:			
Acute infection	Death, hospitalization, antibiotic treatment, or visit to GP due to newly onset infectious disease. Composite outcome.	Categorical, binary	0,1
Death due to infection	Death due to infectious disease.	Categorical, binary	0,1
Hospitalization for infection	Hospital contact due to infectious disease.	Categorical, binary	0,1
Antibiotic treatment	Antibiotic treatment during follow-up.	Categorical, binary	0,1
Doctor diagnosed infection	Infection identified by GP or on-call doctor.	Categorical, binary	0,1
Secondary outcomes:			
Self-reported respiratory infection	Reported respiratory symptoms or disease compatible with respiratory infection.	Categorical, binary	0,1
Verified CoV  infection (first event)	Positive SARS-CoV-2 test.	Categorical, binary	0,1
All-cause hospitalization	Admission to hospital > 24 hours (first event).	Categorical. binary	0, 1

 SARS-CoV-2 infection.

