### **Sample size**

With an expected incidence of “acute infection” of 20% we will be able to show a 25% reduction in the risk of acute infection in the intervention group compared to the placebo group by including a total of 1890 individuals: 945 individuals in each group. Since the primary outcome data to a large extent are obtained via national registers, we anticipate limited loss of power due to loss to follow-up. We therefore aimed to enroll 1900 participants.

Due to the pandemic and varying infectious disease precautions, recruitment took longer than anticipated, and we ended up recruiting a total of 1706 participants (90% of the anticipated sample size) between September 2020 and December 2021.

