### Exclusion/loss to follow-up

Participants who are excluded after randomization or lost to follow up are not replaced. Participants are under follow-up for 12 months post-randomization or until they withdraw their consent, migrate to another country, or die.

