## 6.0 DESCRIPTION OF OUTCOMES AND VARIABLES

### Primary outcome

The primary outcome is a composite outcome: acute infection identified either by a doctor, by antibiotics use, by hospitalization, or by death due to infection. All subcomponents will also be presented separately.

Information on hospitalizations, deaths, and antibiotics use is retrieved from national health registers: The Danish National Patient Register, The Central Person Register, and The National Prescription Register. All hospital contacts due to acute infection will be included, regardless of duration of the contact. An acute infection event identified by a doctor is defined as newly onset infectious illness that has prompted the participant to seek medical attention from general practitioner (GP) or on-call doctor and is based on self-reporting. Participants are asked in the questionnaires, if they have needed to see their GP or an on-call doctor due to newly onset illness during the past 14 days (yes/no). Thus, participants can only have one such event per survey period (14 days). For all outcomes, a honeymoon period of 14 days will be used to define new events.

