#### Primary outcome:

Acute infection will be analyzed as a recurrent time-to-event using an Andersen-Gill Cox proportional hazards regression model with time since inclusion as underlying time scale.

The proportional hazards assumption will be tested using Schoenfeld residuals. The analysis

will be done for the composite outcome and for all the subcomponents separately presenting hazard ratio with 95% confidence intervals for each. Absolute risk reductions will be calculated using Cox regression.

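### The antibiotic component of the Part A primary outcome has no infection limit, so with a 14-day rule and a recurrent-event model, repeat dispensings to continuous users can be counted many times as new acute infections

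*SAP*

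**What the plan says.** All references are to Part A of the SAP.

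- Section 6.0, Variables, antibiotic row: "Antibiotic treatment during follow-up". The death, hospitalization and doctor rows each name infection; this row does not.
- Section 6.0, Variables, composite row: "Death, hospitalization, antibiotic treatment, or visit to GP due to newly onset infectious disease".
- Section 6.0, Primary outcome: the composite is "acute infection identified either by a doctor, by antibiotics use, by hospitalization, or by death due to infection". On sources, "Information on hospitalizations, deaths, and antibiotics use is retrieved from national health registers"; for antibiotics this is the prescription register.
- Same section, on separating events: "For all outcomes, a honeymoon period of 14 days will be used to define new events". It does not say whether the 14 days run from the last counted event, from the latest record, or from the end of treatment.
- Section 7.0, Primary outcome: "Acute infection will be analyzed as a recurrent time-to-event using an Andersen-Gill Cox proportional hazards regression model". The same analysis is repeated for each component.
- Section 5.0 sets 12 months of follow-up.

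**The concern.** The two rows of the same table do not define the same thing. The composite row conveys an intent to count treatment of new infections. The component row, which is what a programmer would apply to register records, takes any antibiotic. Nothing else in the SAP carries the new-onset condition over to those records, and 14 days is shorter than an ordinary refill cycle.

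Any antibiotic is a reasonable register proxy when only the first event counts, because a long-term user then counts once. In a recurrent-event model the same person can add an event at every refill. BCG would not be expected to prevent those events. They pull the hazard ratio toward 1. Because they are concentrated in a few people, they also raise the between-person variance that a correct (robust) standard error has to reflect. Recruitment stopped at 1706, 90% of target, so there is little power to spare.

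**Working it through.** **1. The plan's own figure.** Section 3.0 states "With an expected incidence of “acute infection” of 20% we will be able to show a 25% reduction" with 945 per group. Inputs: 20% versus 0.75 × 20% = 15%, two-sided 5%. Part A states no power; 80% is inferred because it reproduces the figure.

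n′ = [1.96·√(2·0.175·0.825) + 0.8416·√(0.20·0.80 + 0.15·0.85)]² / 0.05² = 905.4, so 906. With continuity correction, n = (n′/4)·[1 + √(1 + 4/(0.05·n′))]² = 944.9, so 945. The figure is reproduced. It is a comparison of proportions, in which each person counts at most once.

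**2. Events one continuous user can contribute in 365 days**, first dispensing on day 0:

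| Refill interval (days) | 14 days from last counted event | 14 days restarting at each dispensing |
|---|---|---|
| 7 | 27 | 1 |
| 10 | 19 | 1 |
| 28 | 14 | 14 |
| 30 | 13 | 13 |
| 90 | 5 | 5 |

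If the 14 days mean time free of treatment, an uninterrupted user contributes 1 event at any interval. The SAP's wording allows all three readings.

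**3. Effect on the primary estimate.** Inputs: n = 1706/2 = 853 per arm and true ratio 0.75 (from the SAP). Assumed: λ = 0.3 acute events per person-year on placebo, gamma frailty variance θ = 1, and a share q of each arm with k unrelated dispensings a year, each counted.

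- Means: m₀ = λ + qk; m₁ = 0.75λ + qk
- Variances: v₀ = λ + θλ² + q(1−q)k²; v₁ is the same with 0.75λ in place of λ
- Observed ratio RR = m₁/m₀; SE = √[v₀/(n·m₀²) + v₁/(n·m₁²)]; power = Φ(|ln RR|/SE − 1.96)

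This takes a robust variance that keeps all of one person's events together. The SAP says only that it clusters on couples.

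Example, q = 1%, k = 12: m₀ = 0.42, m₁ = 0.345, RR = 0.821. v₀ = 0.39 + 0.01·0.99·144 = 1.816 and v₁ = 0.2756 + 1.4256 = 1.701. SE = √(0.01207 + 0.01676) = 0.170. Power = Φ(0.1967/0.170 − 1.96) = Φ(−0.80) = 21%.

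| k per year | q | Share of placebo events unrelated | RR | Power, formula | Power, simulation |
|---|---|---|---|---|---|
| none | 0 | 0% | 0.75 | 77% | 78% |
| 4 | 0.5% | 6% | 0.77 | 67% | 67% |
| 4 | 1% | 12% | 0.78 | 60% | 61% |
| 4 | 2% | 21% | 0.80 | 48% | 49% |
| 12 | 0.5% | 17% | 0.79 | 32% | 34% |
| 12 | 1% | 29% | 0.82 | 21% | 21% |
| 12 | 2% | 44% | 0.86 | 14% | 14% |

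The simulation used 3,000 trials per setting with the same inputs.

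**4. Sensitivity to the event rate.**
- The SAP's 20% implies λ = −ln(0.8) = 0.223. With θ = 0, power is 74% without unrelated events. For q from 0.5% to 2% it falls to 59%-36% (k = 4) or 20%-9% (k = 13).
- At λ = 0.5 and θ = 1, simulated power falls from 90% to 61%, 44% and 30% for monthly refills at q = 0.5%, 1% and 2%.

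**5. Each long-term user counted once.** With k = 1, λ = 0.3 and θ = 1, the same formulas give RR 0.75 to 0.77 and power 76% to 74% for q from 0.5% to 2%. Nearly all the loss comes from repeat counting.

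**The case against.** A reader might infer that the SAP prescribes counting every refill as a new acute infection. It does not. The composite row shows the intent to count only new infection, the SAP never says that each dispensing is an event, and the 14 days could mean treatment-free time, in which case a continuous user counts once. That stands: the fault is a mismatch between rows and an open rule that permit repeat counting. It is not enough to dismiss the point, because the rule is applied to register records and the component row, with its own hazard ratio, has no infection limit under any reading.

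A reader might also infer bias in favour of one arm. The documents give no ground for that. Long-term use is expected to be balanced by randomization, so the cost is dilution and imprecision, not a spurious benefit.

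Nor can the power figures be taken as this trial's power. The SAP gives no prevalence of long-term use, refill frequency, recurrent event rate or frailty, and does not mention refills or prophylaxis. The trial may have few such participants.

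Two further points are fair. Presenting each component separately lets readers see how far antibiotics drive the composite, but it does not repair the composite estimate. Drug codes and extraction rules may sit in the protocol, so their absence is not the point here. The point is that definitions the SAP does state disagree.

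**Conclusion.** The concern holds in limited form. The antibiotic row has no infection limit and conflicts with the composite row. With a 14-day rule of unstated start point and a recurrent-event model, repeat or preventive dispensings can enter many times as new acute infections, both in the composite and, more heavily because fewer other events surround them, in the antibiotic component. The consequence is a ratio pulled toward 1 and a wider interval, equally in both arms in expectation. Under the assumptions in the working, a true 0.75 would be seen as about 0.77 to 0.86, with power between 67% and 14% instead of about 78%. Where the trial falls in that range, or whether the loss is smaller still, cannot be told from the document. It should be settled before the data are analysed.

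**What to change.** 1. Align the two rows so that the antibiotic component means the start of a new treatment course, in the composite and on its own.
2. Merge consecutive dispensings into one course. Let the new-event gap run from the end of the last dispensing's supply. Alternatively, restart it at each dispensing, with a gap longer than the refill cycle. That gap must also cover quarterly refills: 60 days, for instance, would not merge dispensings about 91 days apart.
3. Treat participants on a continuing course at randomization as not at risk for a new antibiotic event until that course ends, while they stay at risk for the other components.
4. Report the any-dispensing version as a sensitivity analysis.

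The cost is SAP wording and recoding of register data already planned. The drawbacks are that some genuine second infections inside the gap are merged, and that a preventive course started after randomization still counts once.

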## 7.0 ANALYSIS

### Methods

All analyses will be performed from the intention-to-treat principle, for all participants studied together and stratified by sex and age group.

Several couples participated in this study. To consider shared vulnerability, we will cluster on couples (non-stratified analysis).

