## 3.0 STUDY METHODS

### Trial design

A single-blinded, placebo controlled randomized clinical trial. Participants are randomized 1:1 to BCG or placebo and will be followed for 12 months post-randomization with respect to illness, medical contacts, use of antibiotics, hospitalization, and death. The follow-up takes place both through self-reporting and through the Danish National Registers. The participants will receive an electronic questionnaire biweekly with questions about illness, medical contacts, other vaccinations, and side effects.

People  $\geq 65$  years of age are eligible for participation.

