### **Randomization**

Randomization takes place at baseline after informed consent is given. The randomization is done in varying blocks of 6-8, stratified by sex and age group (65-74; 75+) using REDCap electronic data capture tools hosted at the Region of Southern Denmark.

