#### **Secondary outcomes:**

The secondary endpoint self-reported respiratory infection will be analyzed the same way as the primary endpoint. As participants are only able to report one infectious episode during a follow-up questionnaire, the event will be assigned to the first day within the questionnaire period, and the following 14 days of follow-up excluded for analyses as it represents risk free time.

The secondary outcomes verified SARS-CoV-2 infection and all-cause hospitalization will be analyzed in a standard Cox proportional hazards model, but otherwise as described above.

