**Table 2 Results primary and secondary outcomes**

Outcome	Number (%)		Hazard ratio (95% CI)	Absolute risk reduction (95% CI)
	BCG N=xxx	Placebo N=xxx		
Primary outcome				
Acute infection	xx (x.x)	xx (x.x)	x.xx (x.xx–x.xx)	x.x% (x.x%–x.x%)
Death	xx (x.x)	xx (x.x)	x.xx (x.xx–x.xx)	x.x% (x.x%–x.x%)
Hospitalization	xx (x.x)	xx (x.x)	x.xx (x.xx–x.xx)	x.x% (x.x%–x.x%)
Antibiotics	xx (x.x)	xx (x.x)	x.xx (x.xx–x.xx)	x.x% (x.x%–x.x%)
Doctor	xx (x.x)	xx (x.x)	x.xx (x.xx–x.xx)	x.x% (x.x%–x.x%)
Secondary outcomes				
Self-reported respiratory infection	xx (x.x)	xx (x.x)	x.xx (x.xx–x.xx)	x.x% (x.x%–x.x%)
Verified COVID-19	xx (x.x)	xx (x.x)	x.xx (x.xx–x.xx)	x.x% (x.x%–x.x%)
All-cause hospitalization	xx (x.x)	xx (x.x)	x.xx (x.xx–x.xx)	x.x% (x.x%–x.x%)

**Table 3 Supplementary analyses to explore possible effect modification by sex, age group, other vaccines, previous BCG, and COVID-19 vaccination status at inclusion.**

	Number (%)		Hazard ratio (95% CI)	Absolute risk reduction (95% CI)
	BCG N=xxx	Placebo N=xxx		
Acute infection – also where numbers permit subdivided on each of the outcomes included in the composite outcome.				
Females	xx (x.x)	xx (x.x)	x.xx (x.xx–x.xx)	x.x% (x.x%–x.x%)
Males	xx (x.x)	xx (x.x)	x.xx (x.xx–x.xx)	x.x% (x.x%–x.x%)
Age < 75	xx (x.x)	xx (x.x)	x.xx (x.xx–x.xx)	x.x% (x.x%–x.x%)
Age ≥ 75	xx (x.x)	xx (x.x)	x.xx (x.xx–x.xx)	x.x% (x.x%–x.x%)
Other vaccines received after randomization:				
Effect of intervention before other vaccines	xx (x.x)	xx (x.x)	x.xx (x.xx–x.xx)	x.x% (x.x%–x.x%)
Effect of intervention after other vaccines	xx (x.x)	xx (x.x)	x.xx (x.xx–x.xx)	x.x% (x.x%–x.x%)
Effect after other vaccines, by type of vaccine received:				
COVID vaccine	xx (x.x)	xx (x.x)	x.xx (x.xx–x.xx)	x.x% (x.x%–x.x%)
Influenza vaccine	xx (x.x)	xx (x.x)	x.xx (x.xx–x.xx)	x.x% (x.x%–x.x%)
Both vaccines	xx (x.x)	xx (x.x)	x.xx (x.xx–x.xx)	x.x% (x.x%–x.x%)
Has BCG scar 	xx (x.x)	xx (x.x)	x.xx (x.xx–x.xx)	x.x% (x.x%–x.x%)
No BCG scar 	xx (x.x)	xx (x.x)	x.xx (x.xx–x.xx)	x.x% (x.x%–x.x%)
CoV vaccinated before enrollment:				
Yes	xx (x.x)	xx (x.x)	x.xx (x.xx–x.xx)	x.x% (x.x%–x.x%)
No	xx (x.x)	xx (x.x)	x.xx (x.xx–x.xx)	x.x% (x.x%–x.x%)
Included period 1 	xx (x.x)	xx (x.x)	x.xx (x.xx–x.xx)	x.x% (x.x%–x.x%)
Included period 2 	xx (x.x)	xx (x.x)	x.xx (x.xx–x.xx)	x.x% (x.x%–x.x%)

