#### Primary outcome:

Mean change in GMT in samples from day 14 and 42 will be compared between the control group and the three treatment groups in linear regression analyses with adjustment for baseline level of GMT, age group, and sex. In case residuals are not normally distributed, the analysis will be performed on log-10 transformed change in GMT instead. The proportion of participants who seroconvert will be compared in logistic regression analysis with adjustment for age group and sex.

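### Part A randomizes within sex and age group, but on the likeliest reading its overall Cox models leave both factors out, giving up a little precision that costs almost nothing to keep

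*SAP*

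**What the plan says.** - **Randomization (Part A, section 3.0):** allocation is 1:1 in blocks of varying size within four strata, sex by age group (65 to 74; 75 and over).
- **Methods (Part A, section 7.0):** all analyses follow intention to treat, "for all participants studied together and stratified by sex and age group". The next paragraph deals with couples: "we will cluster on couples (non-stratified analysis").
- **Primary model (Part A, section 7.0):** an "Andersen-Gill Cox proportional hazards regression model with time since inclusion as underlying time scale". No covariate or stratum is named.
- **First-event secondary outcomes (Part A, section 7.0):** SARS-CoV-2 infection and all-cause hospitalization "will be analyzed in a standard Cox proportional hazards model, but otherwise as described above". Again no covariate or stratum is named.
- **Table shells (Part A, section 8.0):** Table 2 has one overall hazard ratio per outcome. Females, males, under 75 and 75 or over are separate rows of Table 3, titled "Supplementary analyses to explore possible effect modification by sex, age group, other vaccines".
- **Part B (section 14.0):** the Methods sentence on sex and age group is repeated. The model for antibody change is then specified separately "with adjustment for baseline level of GMT, age group, and sex", and the seroconversion model is adjusted for age group and sex.

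**The concern.** When randomization is stratified on prognostic factors, the design removes chance imbalance in them between the arms. An analysis that leaves the factors out does not use that balance: its standard error still carries the between-stratum variation, so the test tends to be conservative. Sex and age group are known for everyone randomized, so using them needs no new data. Enrolment ended at 1706 against a calculated requirement of 1890, which is a reason to keep small gains.

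The wording is a second problem. The SAP uses the one word for how participants were randomized and, apparently, for how subgroup results are reported. Two analysts could fit different primary models from the same sentence.

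**Working it through.** **1. What the wording most likely means.** Four features point to subgroup results and not to a stratified Cox model.
- The Methods sentence joins a pooled analysis and a stratified one with "and", which describes two sets of results.
- Clustering on couples is tied to the non-stratified analysis, so a pooled, non-stratified analysis exists. The restriction makes sense if the stratified results are separate by sex, because mixed-sex couples would then be split.
- Table 3 gives sex and age group as separate rows, under effect modification.
- Part B repeats the sentence and still adds adjustment model by model, so the sentence was not meant to supply it.

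**2. The plan's own sample size.** Inputs from section 3.0: 20% risk under placebo and a 25% reduction, so 15% under BCG. Section 4.0 gives two-sided 0.05. Part A states no power; 80% is assumed.

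n = [1.960·√(2·0.175·0.825) + 0.842·√(0.20·0.80 + 0.15·0.85)]² / 0.05² ≈ 905.4, so 906 per group.

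With continuity correction: (905.4/4)·[1 + √(1 + 4/(905.4·0.05))]² ≈ 945 per group.

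This matches the SAP's 945. It is an unadjusted calculation and does not change here.

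**3. First-event outcomes.** Simulated trials, 4,000 per setting: 1706 participants, 12 months, hazard ratio 0.75, blocks of 6 or 8 within four strata, and a baseline hazard set to a 20% one-year risk at the average rate. Assumed because the SAP does not give them: 50% female, 30% aged 75 or over, and the prognostic hazard ratios. The unstratified log-rank test is compared with the stratified one.

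| Assumed HR, sex / age | Power, unstratified → stratified | Type I error, unstratified → stratified |
|---|---|---|
| 1.0 / 1.0 | 68.7% → 68.8% | 5.3% → 5.2% |
| 1.25 / 1.5 | 70.2% → 70.6% | 5.2% → 5.1% |
| 1.5 / 2.0 | 67.4% → 68.5% | 5.3% → 5.4% |
| 2.0 / 3.0 | 65.9% → 69.0% | 4.2% → 5.1% |

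The Monte Carlo standard error is √(0.69·0.31/4000) ≈ 0.7 points for power and √(0.05·0.95/4000) ≈ 0.3 points for type I error. Only the contrast within a row matters, since both tests use the same simulated trials. A separate set of 2,000 trials per setting gave 68.6% → 69.1% at 1.3 / 1.6 and 70.6% → 71.7% at 1.5 / 2.0.

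**4. Recurrent primary outcome.** Let μ be events per person-year, c² the squared coefficient of variation of the rate between strata, and θ the residual frailty variance. The robust variance is proportional to 1 + μ[c² + θ(1 + c²)], and accounting for the strata removes μc². A 20% risk corresponds to μ = −ln(0.80) ≈ 0.22.

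Example at 1.5 / 2.0: c² = (1.625/1.5625)·(1.9/1.69) − 1 = 0.169. With θ = 0 the ratio is 1/(1 + 0.22·0.169) = 0.964.

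| Assumed HR, sex / age | c² | Variance ratio at μ = 0.22 (θ = 0; 1) | Variance ratio at μ = 0.5 (θ = 0; 1) |
|---|---|---|---|
| 1.25 / 1.5 | 0.053 | 0.989; 0.991 | 0.974; 0.983 |
| 1.5 / 2.0 | 0.169 | 0.964; 0.971 | 0.922; 0.949 |
| 2.0 / 3.0 | 0.476 | 0.905; 0.927 | 0.808; 0.880 |

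At μ = 0.22 the reported variance falls by about 1 to 9%. The confidence interval on the log scale narrows by 1 − √0.991 ≈ 0.5% to 1 − √0.905 ≈ 5%.

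**5. Is the primary hazard ratio attenuated?** With recurrent events and balanced strata, the unadjusted Andersen-Gill ratio is close to a ratio of mean rates. With a true ratio of 0.75, 14-day risk-free gaps, sex / age hazard ratios from 1.3 / 1.6 to 2 / 3, and 0.22 or 0.5 events per year, simulation of 6 million persons per setting gave unadjusted ratios of 0.749 to 0.753. There is no material attenuation.

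**The case against.** The strongest reply is that this is an ambiguous word plus a modelling preference. The SAP nowhere says that the overall model ignores the strata, and the Methods sentence could be read as a stratified Cox model. That stands as far as it goes: the omission is an inference, although a well-supported one. It does not remove the need for a change, because on either reading the primary model should be stated.

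Three stronger readings might be inferred, and the SAP does not support them.
- **That the primary hazard ratio is pulled toward 1.** This applies only to the first-event secondary outcomes, where the marginal and conditional hazard ratios differ. That is a difference of estimand and not an error. In those models adjustment raises power mainly by moving the estimate, not by narrowing the interval.
- **That Part B shows a slip in Part A.** Part B adjusts its antibody and seroconversion regressions. Its own randomized Andersen-Gill comparison of infections names no adjustment; the sex and age adjustment in that section belongs to the antibody-titre association. The two parts treat randomized Cox comparisons alike.
- **That both factors are known to be strongly prognostic here.** The SAP's background says that infection risk is raised in the elderly. It gives nothing on sex, or on 65 to 74 against 75 and over.

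It is also fair to object that a four-stratum Cox model has four baseline hazards, so the absolute risk reduction planned for every row of Table 2 needs an averaging rule.

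**Conclusion.** The point holds as a free improvement. On the likeliest reading, the overall Part A models leave out the two factors used to stratify randomization. The planned analysis remains valid: type I error is not inflated and the sample size is unaffected. At most the test is slightly conservative, with type I error of 4.2% in the strongest setting.

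The loss is about 0 to 1 power point with moderate factors and about 3 points with strong ones for first-event outcomes. For the recurrent primary outcome it is about 1 to 9% of the robust variance at about 0.22 events per person-year, and more if events are commoner. If the factors are not prognostic, nothing is lost by including them. These sizes rest on assumed prognostic hazard ratios, an assumed mix of sex and age, and a residual frailty variance of 0 or 1. The direction does not depend on the exact values.

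**What to change.** In Part A section 7.0:
- State that all overall Andersen-Gill and standard Cox models are stratified by, or adjusted for, sex and age group as randomized. Name which of the two will be used.
- Keep the clustering on couples. A robust variance summed by couple still works when partners fall in different strata.
- State that the absolute risk reduction is obtained by predicting risk under each arm within each stratum and averaging over the observed stratum distribution.
- Call the by-sex and by-age results subgroup analyses in Methods, so that "stratified" has one meaning.

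The cost is a few lines of text, one option or term in each model and the averaging step for the absolute risk reduction. No new data are needed.

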### **Secondary outcomes**

*Self-reported infections:*

Infections are identified through information given by the participants in the electronic follow-up questionnaires, where they are asked to describe disease episodes every 14 days. They are asked if they have been ill, and then asked to cross off their symptoms on a list. Furthermore, we ask them to provide the most likely cause for their illness. Disease episodes are characterized as infections if participants report symptoms compatible with an infectious disease or they report an infectious disease diagnose as the cause of their illness. Criteria for self-reported infection:

- Having one or more of the following symptoms: fever, cough, sore throat, runny nose/nasal congestion (common cold symptoms), loss of smell or taste sense, vomiting, or diarrhea with or without general symptoms such as headache, myalgia, dysarthria, or fatigue.
- Having dyspnea AND fever with or without general symptoms such as headache, myalgia, dysarthria, or fatigue.
- Having described an infectious disease as the self-estimated cause of illness. This is a free-text field and participants answers will be classified as infectious disease or not by medically trained study personnel.

Baseline for analysis is set at day 14 reflecting completion of the allocated vaccinations. We will however also conduct the analysis from day 0-14. Participants can register a maximum of one infectious disease event per survey period (14 days).

A secondary analysis of association between influenza antibody level and subsequent risk of infection will be performed to test if high antibody titers correlate with risk of infection.

*Immunological outcomes (subgroup analyses):*

A random subset of participants (the first to accept) have extra blood samples taken for further immunological analyses.

1. Lymphocyte-dependent responses 7 days after influenza vaccination
2. The induction of innate immune memory 14- and 42-days post-randomization

For the lymphocyte analyses, 10 participants from groups 1-3 will have blood drawn on day 21, exactly 7 days after influenza vaccination. We will assess the effect of the different treatment combinations on the response to the influenza vaccine, examining activated

influenza antibody-secreting B-lymphocytes. Due to the different timing of the influenza vaccination, participants from group 4 are not part of this analysis.

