## 14.0 ANALYSIS

### Methods

All analyses will be performed from the intention-to-treat principle, for all participants studied together and stratified by sex and age group.

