#### Secondary outcomes:

##### *Self-reported infections:*

The hazard ratio of infections will be estimated using an Andersen-Gill Cox proportional hazards regression model with infections included as recurrent events and time since inclusion as underlying time scale. The proportional hazards assumption will be tested using Schoenfeld residuals. As participants are only able to report one infectious episode during a follow-up questionnaire, the event will be assigned to the first day within the questionnaire period, and the following 14 days of follow-up excluded for analyses as it represents risk free time.

Association between influenza antibody titer level at day 42 and rate of infections will also be explored in Andersen-Gill Cox proportional hazards regression model, using antibody titer at day 42 as exposure and self-reported infections after day 42 as outcome. Antibody titers will be categorized into quartiles or similar relevant categories. The analysis will be adjusted for sex and age group.

Absolute risk reduction will be calculated using Cox regression.

*Immunological outcomes (subgroup analyses):*

Mean change in number of activated B-cells, concentration of cytokines, as well as fold change in cytokine concentration after stimulation from day 0 to day 14 and from day 14 to day 42 will be compared between the control group and the three treatment groups in linear regression analyses. With and without adjustment for responses in the control condition.

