**Table 1: Baseline characteristics.**

	Group 1	Group 2	Group 3	Group 4
Age, median (IQR)				
Sex female (%)				
Living alone (%)				
Spouse included in study (%)				
Active smoker (%)				
Previous smoker (%)				
Alcohol consumption, units per week, mean (SD)				
BMI, median (IQR)				
Chronic diseases				
Cardiovascular (%)				
Diabetes (%)				
Lung (%)				
Other (%)				
Level of education				
Low (%)				
Medium (%)				
High (%)				
Previously BCG vaccinated (%)				
Scar from BCG vaccination observed (%)				
COVID-19 vaccinated, yes (%) 				
One dose				
Two doses				
Three doses				

 COVID-19 vaccinated before enrollment.

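### The SAP's only clustering rule stops at Part A's non-stratified analysis, so the Andersen-Gill models by sex and age group and both Part B infection models state no allowance for repeat events in one person

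*SAP*

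**What the plan says.** Part A, section 7.0, Methods, plans every analysis both overall and by subgroup: "All analyses will be performed from the intention-to-treat principle, for all participants studied together and stratified by sex and age group". It then gives the clustering rule: "To consider shared vulnerability, we will cluster on couples (non-stratified analysis").

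The Part A primary outcome is a recurrent-event analysis: "Acute infection will be analyzed as a recurrent time-to-event using an Andersen-Gill Cox proportional hazards regression model". Self-reported respiratory infection is to be handled in the same way. A person can contribute several events, because a new event is defined by a gap: "For all outcomes, a honeymoon period of 14 days will be used to define new events".

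Part B, section 14.0, Methods, repeats the sentence on intention to treat and stratification but has no sentence on clustering. Its secondary outcomes use two recurrent-event models. The first compares the randomised groups: "The hazard ratio of infections will be estimated using an Andersen-Gill Cox proportional hazards regression model with infections included as recurrent events". The second relates antibody level to later infection, "using antibody titer at day 42 as exposure and self-reported infections after day 42 as outcome". Section 13.0 allows repeat events here too: "Participants can register a maximum of one infectious disease event per survey period (14 days"). Part B's baseline table has a row for "Spouse included in study", so couples are expected there as well.

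Neither part names a robust variance, a person-level cluster or a frailty term for these models.

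**The concern.** An Andersen-Gill model with model-based variance treats each event as independent information, given the covariates. If some people are more infection-prone than others, events in one person are correlated and the model-based standard error is too small. Confidence intervals are then too narrow, and differences reach the two-sided 0.05 level too often.

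In Part A's pooled analysis the couple rule deals with this. A couple cluster holds all events of both spouses, and a single participant forms a cluster of one. The bracketed restriction means that the rule does not reach the analyses by sex and age group. Part B cannot easily be read as inheriting it. Where Part B borrows from Part A (screening, recruitment, section 12.0) it says so, whereas its Methods paragraph restates Part A's first sentence and leaves out the clustering.

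At stake are reported hazard ratios with 95% intervals in Part A's Table 3 and Part B's Table 3.

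**Working it through.** **1. Which results are affected.**
- Part A Table 3: two recurrent outcomes (composite acute infection, self-reported respiratory infection) × four rows (females, males, under 75, 75 and over) = 8 rows. If numbers permit subdivision, three recurrent components (hospitalization, antibiotics, doctor) × 4 add up to 12.
- Part B: the randomised-group model and the day-42 quartile model.
- Not affected by this problem: death, the first-event Cox outcomes, Part A's pooled results, and Part B's day 0-14 analysis (one event at most).
- Not counted: Part A's other subgroup rows (vaccines, BCG scar, inclusion period). They use the methods described above them, and whether that includes couple clustering is unclear.

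**2. The SAP's own event figure.** Part A's sample size uses 20% against 15% (a 25% reduction). With two-sided alpha 0.05 and 80% power (assumed, as Part A's sample-size text states none), n = [1.96√(2 × 0.175 × 0.825) + 0.842√(0.20 × 0.80 + 0.15 × 0.85)]² / 0.05² gives 906 per group, and 945 with continuity correction. This matches the SAP. The 20% is its only event figure for Part A; it gives no recurrent rate.

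**3. Closed form.** Let a person's rate be multiplied by a gamma frailty with mean 1 and variance θ, and let μ be the mean number of events. The count has variance μ + θμ², while the model assumes μ, so the variance is inflated by 1 + θμ. For 20% ever infected, (1 + θμ)^(−1/θ) = 0.8, so 1 + θμ = 0.8^(−θ).
- θ = 0.5: inflation 1.118; type I error 2[1 − Φ(1.96/√1.118)] = 6.4%; correct interval √1.118 = 1.06 times as wide.
- θ = 1.0: inflation 1.25; type I error 8.0%; 1.12 times as wide.

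**4. Simulation under no effect, Part A stratum of half the sample.** 1706/4 ≈ 426 per arm (assumed; the SAP gives no stratum sizes). The first version runs in continuous time over 365 days with 14 days out of risk after each event (4,000 trials). The second uses 26 windows of 14 days with at most one event each (20,000 trials). Entries are type I error with model-based variance for θ = 0 / 0.5 / 1.0.

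| Events | Continuous time | 14-day windows | Correct ÷ model-based interval width (θ = 0.5 / 1.0) |
|---|---|---|---|
| 20% ever infected | 5.0 / 6.5 / 7.0% | 4.9 / 6.4 / 7.7% | 1.05 / 1.10 |
| mean 0.5 (assumed) | 5.5 / 8.1 / 10.7% | 4.6 / 7.8 / 10.2% | 1.11 / 1.20 |
| mean 1.0 (assumed) | 4.4 / 11.5 / 15.7% | 4.7 / 9.8 / 15.4% | 1.20 / 1.37 |

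With 200 per arm and 20% ever infected the result is 4.5 / 6.0 / 7.5%, so stratum size matters little.

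**5. Part B, same θ values.** All event rates are assumed.
- Group comparison, 68 per arm (75 less 10%), 12 windows: 4.4 / 6.4 / 8.9% at 0.5 events; 3.8 / 8.7 / 13.4% at 1.0; 3.5 / 10.4 / 15.3% at 1.5.
- Quartiles, 67 each, 10 windows after day 42: 4.2 / 6.6 / 8.9% at 0.5 events; 3.5 / 9.2 / 13.6% at 1.25.

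**6. Effect of the remedy.** Robust variance clustered on the person gave 4.3-5.7% in the runs of steps 4 and 5. For an age-group row at 20% ever infected, with an assumed 30% of people in couples sharing one frailty of variance 1.0, type I error was 7.9% model-based, 5.2% clustered on the person and 5.1% clustered on the couple. The person level does nearly all the work.

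**The case against.** The strongest reply is that this is silence, not a wrong choice. The rule's stated purpose is dependence between spouses, and the bracket limits that alone. It has an innocent explanation, since stratifying by sex separates opposite-sex spouses. Many analysts fit Andersen-Gill models with robust variance by habit. A reader might infer that the SAP chose model-based variance for these rows; it does not, because the estimator is unstated. That part of the objection stands and limits the point. It does not remove it: the age-group rows can hold both spouses, and separating spouses is no reason to leave one person's repeat events unclustered. An analyst applying the plan literally would fit these models without clustering.

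It may also be said that the 14-day rule already handles repeats. That rule fixes what counts as a new event and which time is at risk. It does nothing about correlation between one person's events weeks apart.

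The reach is small. The Part A rows explore effect modification, the quartile model is exploratory, and Part B's sample-size section concedes that only pronounced clinical differences could be shown. The component rows are conditional on numbers and, being no more frequent than the composite, would be inflated less at the same θ. All of this stands and sets the weight.

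**Conclusion.** The point holds as a gap in what the plan fixes, at low severity. Followed as written, Part A's Andersen-Gill rows by sex and age group and Part B's two infection models make no allowance for repeat events in one person.

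The direction (intervals too narrow) follows if model-based variance is used and people differ in infection-proneness. The size rests on an assumed frailty variance of 0.5 to 1.0: about 6-8% type I error and intervals that should be 5-10% wider at the SAP's 20%, and about 8-11% at an assumed 0.5 events per person. The larger figures in the working need event rates that the SAP does not give and should not drive the weight. With no heterogeneity there is no inflation.

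A reader might infer that the primary analysis shares the fault. It does not: couple clusters in the pooled Part A analysis contain each person's events, and Part B's primary outcome is antibody response, not recurrent events.

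**What to change.** Keep Part A's couple rule for all pooled models, including the first-event Cox models for verified SARS-CoV-2 infection and all-cause hospitalization, which inherit it from the general methods. The new sentences are additions and must not replace it.

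- Part A, section 7.0, Methods, add: *Andersen-Gill models run by sex or age group use robust variance clustered on the participant (on the couple where both spouses are in the model).*
- Part B, section 14.0, Secondary outcomes, add: *Both Andersen-Gill infection models use robust variance clustered on the participant (on the couple where both spouses are in the model).*

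The cost is one sentence in each part and one software option. Some subgroup and Part B intervals become modestly wider, by about 5-10% in Part A subgroups at 20% incidence and frailty variance 0.5 to 1.0.
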